6.3 SUBJECT SETS ANALYSED

Enrolled set (ES):

This subject set includes all patients who were enrolled in the study regardless of whether they were treated or not. The ES is used for the disposition tables / listings and the disclosure tables for enrolment.

Section 7.3 of the CTP:

Treated set (TS)

The treated set includes all patients who were randomized and treated with at least one dose of study drug (either treatment with BI 764524 or Sham).

Biomarkers

Section 7.3.3.2 of the CTP:

Biomarker set (BMS):

Biomarker data and parameters of a patient will be included in the statistical biomarker (BM) analyses if they are not flagged for exclusion due to a protocol deviation relevant to the evaluation of biomarkers (to be decided no later than in the Report Planning Meeting) or due to non-evaluability.

Exclusion of a patient's data will be documented in the CTR.

Biomarker data and parameters of a patient which is flagged for exclusion will be reported with its individual values but will not be included in the statistical analyses.

Table 6.3: 1 Subject sets analysed

Class of endpoint	ES	TS	PKS	BMS
Primary endpoints		X		
Analysis of PK endpoints			X	
Analysis of PD endpoints/biomarkers				X
				
Other secondary and further endpoints		X		
Safety parameter		X		
Demographic/baseline parameter		X		
Important protocol deviations		X		
Disposition/Disclosure (enrolment)	X			

6.5 POOLING OF CENTRES

Due to the limited number of patients, all patients will be pooled without using different weights for centres.

6.6 HANDLING OF MISSING DATA AND OUTLIERS

Handling of missing data and outliers will be performed as described in the CTP, Section 7.5.

Imputation might be necessary for AE dates in the safety evaluation. Missing or incomplete AE dates are imputed according to BI standards (see BI-KMED-BDS-HTG-0035 (7)).

Missing time at unscheduled ocular assessment performed on the day of administration are regarded as on treatment. The missing time will be imputed and set to 23:59 at the day of administration.

Missing data and outliers of PK data are handled according to BI standards.

Missing baseline laboratory values will be imputed by the respective values from screening.

If single cardiac cycles of an ECG (out of the generally four) are missing, the arithmetic mean for this single ECG will be computed with the reduced (1, 2 or 3) number of cardiac cycles.

If replicate ECG recordings are missing, the arithmetic means per time point will be computed with the reduced number (1 or 2) of recordings.

For the classification of the on-treatment QTc/QT intervals into “no new onset” / “new onset” categories, a missing value is obtained only in case that

- (i) all on-treatment values are missing and
- (ii) the baseline value is less than or equal to 500 msec, or missing.

If condition (i) is fulfilled but the baseline value is greater than 500 msec, this case will be categorized as ‘no new onset’. If baseline is missing and the maximum on treatment QTc interval is greater than 450 msec (or 500 msec for QT interval, respectively), this is classified as a ‘new onset’ in the respective category. If baseline is missing and the maximum QTc interval is less than or equal to 450 msec (or 500 msec for QT interval, respectively), this will be categorized as ‘no new onset’. If baseline is missing, a QTc/QT interval > 500 msec at any time on treatment will be a notable finding.

6.7 BASELINE, TIME WINDOWS AND CALCULATED VISITS

The baseline value is defined as the last measurement before first administration of trial medication (= value at V2, in case no actual time is given in data).

Section 5.1 of the CTP:

For the endpoints, baseline is defined as the value at Visit 2; if not measured at Visit 2 then baseline is the value at Visit 1.

This rule will also apply to the additional endpoint, [REDACTED].

Section 6.1 of the CTP:

For visit schedule, refer to Flow Chart I and Flow Chart II. The acceptable time windows for visits are given in the Flow Charts. For planned individual serum concentration sampling times, refer to appendix 10.1.

SRD Part:

Adherence to time windows will be checked via the consistency check listings at the RPM/DBLM.

MD Part:

Analysis of AE data, potentially clinically significant abnormal laboratory values, concomitant medication or non-drug therapies, as well as use of rescue therapy will not be based on visits. Therefore, no assignment to time windows will be necessary for such data.

All other safety and efficacy measurements will be assigned to visits based on extended time windows around the planned visit dates, defined relative to the day of first trial treatment (which is scheduled for Visit 2). These extended time windows are defined in [Table 6.7: 1](#), [Table 6.7: 2](#), and [Table 6.7: 3](#).

Only one observation per time window will be selected for statistical analysis at a particular visit – the value which is closest to the protocol planned visit day will be selected, except for safety lab where the worst scenario is chosen. If there are two observations which have the same difference in days to the planned day, the later value will be selected.

For [REDACTED], the worst case scenario will be used (i.e. highest value will be taken) if more than one measurement is made in the same time window.

Section 5.2.5.1 of the CTP:

Central ECG lab evaluation will be performed for all ECGs indicated in the Flow Chart I and Flow Chart II. For all ECGs this will include the intervals RR, PR, QRS and QT measured semi-automatically. The screening ECGs will be checked for abnormalities.

The baseline value of an ECG variable is defined as the mean of the ECG measurements prior to drug administration.

Unscheduled measurements of laboratory data will be assumed to be repeat measurements of the most recent scheduled measurement (e.g. for follow-up or confirmation of a particular value). Therefore, unscheduled measurements will be assigned to the planned time point of the previous scheduled measurement.

Table 6.7: 1 Time window assignment of efficacy, safety lab, pk and vital signs measurements to visits for statistical analysis of the MD Part

Visit number (CTP)	Visit label (analysis)	Planned Day	Time window [days]		
			Window per CTP	Start (extended)	End (extended)
V2	Baseline	1	± 0	NA	1
V3	Week 4	29	± 3	2	43
V4	Week 8	57	± 3	44	71
V5	Week 12	85	± 7	72	99
V6	Week 16	113	± 7	100	134
V7	Week 22/EoS	155	+7	135	End of Trial visit date

Days are counted relative to the day of first treatment, which is defined as Day 1.

Table 6.7: 2 Time window assignment 12 lead ECG measurements to visits for statistical analysis of the MD Part

Visit number (CTP)	Visit label (analysis)	Planned Day	Time window [days]		
			Window per CTP	Start (extended)	End (extended)
V2	Baseline	1	± 0	NA	1

Visit number (CTP)	Visit label (analysis)	Planned Day	Time window [days]		
			Window per CTP	Start (extended)	End (extended)
V3	Week 4	29	± 3	2	43
V4	Week 8	57	± 3	44	71
V5	Week 12	85	± 7	72	End of Trial visit date

Days are counted relative to the day of first treatment, which is defined as Day 1.

Table 6.7: 3 Time window assignment physical examination measurements to visits for statistical analysis of the MD Part

Visit number (CTP)	Visit label (analysis)	Planned Day	Time window [days]		
			Window per CTP	Start (extended)	End (extended)
V1	Baseline	... -1	NA	NA	1
V5	Week 12	85	± 7	2	End of Trial visit date

Days are counted relative to the day of first treatment, which is defined as Day 1.

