## **6.2.2 Treatment period(s)**

For the SRD part, masking is not required for the IVT injection preparation or administration. For the MD part, IVT injection will be prepared by the unmasked pharmacist (qualified person). For the MD part, an unmasked injector with no other involvement in the trial will administer either active or sham injection according to the treatment assigned by IRT. IVT injections must be carried out according to medical standards and applicable guidelines by a qualified physician experienced in administering IVT injections and will be done as part of drug administration visit procedures (Visit 2 for SRD part and Visits 2, 3 and 4 for MD part) after the other ophthalmologic assessments in the [Flow Chart I](#) and [Flow Chart II](#) have been performed (please see Section [4.1](#) for details).

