## 10. APPENDICES

### 10.1 TIME SCHEDULE FOR PHARMACOKINETIC (PK) AND ADA BLOOD SAMPLING AND AQUEOUS SAMPLING

Table 10.1: 1 Time schedule for PK and [REDACTED] sampling (SRD part)

Course	Visit	Day/ Week	Planned Time	Planned Time [h]	PK BI 764524	[REDACTED]
1	V2	1	Before drug administration of BI 764524*	-0:30	X	X
	V2	1	Drug administration	0:00		
	V2	1	30 min after drug administration*	00:30	X	
	V3	4 (+/- 1 day)	3 days after drug administration	72:00	X	
	V4	8 (+/- 2 day)/ Week 1	1 week after drug administration	168:00	X	
	V5	15 (+/- 2 day)/ Week 2	2 weeks after drug administration	336:00	X	X
	V6	29 (+/- 3 day)/ Week 4	4 weeks after drug administration	672:00	X	X
	V7	57 (+/- 7 day)/ Week 8	8 weeks after drug administration	1344:00	X	
EOS	V8	99 (+/- 7 day)/ Week 14	12 weeks after drug administration	2016:00	X	X**

\* A time window of +/-15 min for sample drawing is allowed.

\*\*If there is [REDACTED] occurrence a further follow-up will be conducted.

Table 10.1: 2 Time schedule for PK and [REDACTED] blood sampling (MD part)

Course	Visit	Day/ Week	Planned Time	Planned Time [h]	PK BI 764524	[REDACTED]
1	V2	1*	Before drug administration of BI 764524	-0:30	X	X
	V2	1	First Drug administration	0:00		
	V3	29 (+/- 3 day)*/ Week 4	4 weeks after first drug administration; predose to 2 nd drug administration	671:30	X	X
	V3	29(+/- 3 day)/ Week 4	Second Drug administration	672:00		
	V4	57 (+/- 3 day)*/ Week 8	8 weeks after first drug administration; predose to 3 rd drug administration	1343:30	X	
	V4	57 (+/- 3 day)/ Week 8	Third Drug administration	1344:00		
Follow Up Period	V5	85 (+/- 7 day)/ Week 12	12 weeks after first drug administration	2016:00	X	X**
Follow Up Period	V6	113 (+/- 7 day)/ Week 16	16 weeks after first drug administration	2688:00	X	
Follow Up Period	V7	155 (+/- 7 day)/ Week 22	22 weeks after first drug administration	3360:00	X	

\*A time window of 30 mins to 2 hrs before dosing is allowed for sample drawing. PK and [REDACTED] samples must be taken before next drug administration; no window afterwards.

\*\*If there is [REDACTED] occurrence a further follow-up will be conducted.

Table 10.1: 3 Time schedule for optional Aqueous sampling (MD part)

Trial Periods	Visit	Day	Time Point	Optional Aqueous sampling
Treatment	2	1	Just before drug administration	X*
	3	29 (±3)		
	4	57 (±3)	Just before drug administration	X*
Follow-up	5	85 (±7)		
Follow-up	6	113 (±7)	Any time during the visit	X*
EOS	7	155 (±7)	Any time during the visit	X*

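### At Visits 3 and 4 of the MD part, the SAP's closest-day, later-value rule can replace the scheduled pre-injection eye assessment with an unscheduled post-injection one

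*SAP*

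**What the plan says.** **Selection rule (SAP 6.7, MD part).** After exempting AEs and a few other data types, the SAP states: "All other safety and efficacy measurements will be assigned to visits based on extended time windows around the planned visit dates". One observation is kept per window: "the value which is closest to the protocol planned visit day will be selected, except for safety lab where the worst scenario is chosen". For ties: "If there are two observations which have the same difference in days to the planned day, the later value will be selected". For eye data after baseline, nothing separates scheduled from unscheduled values, or values before that visit's injection from values after it.

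**Windows (SAP Table 6.7: 1).** Visit 3 has planned Day 29 and extended window Days 2 to 43. Visit 4 has planned Day 57 and extended window Days 44 to 71. The protocol allows ±3 days at both.

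**Order on injection days (Protocol 6.2.2).** At Visits 2, 3 and 4 the injection is given "after the other ophthalmologic assessments in the" flow charts. Protocol 6.2 also requires BCVA before pupil dilation.

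**Unscheduled assessments.** Protocol 6.2.3 allows unscheduled visits at any time for safety reasons, with any assessment the investigator thinks necessary. SAP 6.6 foresees unscheduled eye assessments on a day of administration that have no recorded time, and treats them as on treatment: "The missing time will be imputed and set to 23:59 at the day of administration".

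**Protection given to other data.** Baseline must precede the first administration (SAP 6.7). Unscheduled laboratory values have their own assignment rule (SAP 6.7). Unscheduled ECGs are left out of the interval analysis (Protocol 5.2.5.1).

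**The concern.** Under the protocol, the scheduled Week 4 and Week 8 eye values are taken just before the second and third injections. A value taken after that day's injection is a different measurement. If it is on the same day, the eye has usually been dilated and has been through the injection or sham procedure. If it is some days later, it follows one more dose than the scheduled value does. Both kinds fall in the same analysis window as the scheduled value, and the rule chooses between them by date and then by lateness.

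Change from baseline in BCVA and in central retinal thickness at Visits 3 and 4 are named secondary endpoints (SAP 5.2.2). SAP 7.5.2 analyses both with an MMRM that has a separate treatment effect at each visit, so a substituted value enters those Week 4 and Week 8 estimates directly. Unscheduled visits are made for safety reasons, so the values that displace scheduled ones need not be typical of the patient.

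**Working it through.** **Step 1. Reproduce the windows.** The extended window ends in SAP Table 6.7: 1 are midpoints of adjacent planned days:
- Visit 3: (29 + 57)/2 = 43
- Visit 4: (57 + 85)/2 = 71
- Visit 5: (85 + 113)/2 = 99
- Visit 6: (113 + 155)/2 = 134

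All four match. The allowed injection days, 26 to 32 and 54 to 60, lie well inside the Visit 3 and Visit 4 windows, so pre-injection and post-injection values compete in one window.

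**Step 2. Write the rule as a formula.** Let P be the planned day, v the day of the scheduled assessment and injection, and u ≥ v the day of an unscheduled post-injection assessment. The unscheduled value is selected when |u − P| ≤ |v − P|, because it is nearer or it ties and is later.
- If v < P, this holds for u from v to 2P − v.
- If v ≥ P, it holds only for u = v.

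**Step 3. Apply it.**

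| Visit 3 held on | Unscheduled days that win | Visit 4 held on | Unscheduled days that win |
|---|---|---|---|
| 26 | 26 to 32 | 54 | 54 to 60 |
| 27 | 27 to 31 | 55 | 55 to 59 |
| 28 | 28 to 30 | 56 | 56 to 58 |
| 29 to 32 | same day only | 57 to 60 | same day only |

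Example: visit and injection on Day 27, unscheduled check on Day 30. The distances are |27 − 29| = 2 and |30 − 29| = 1, so the Day 30 value becomes Week 4.

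Per visit, 7 + 5 + 3 + 1 + 1 + 1 + 1 = 19 day pairs give a post-injection value, out of 18 + 17 + 16 + 15 + 14 + 13 + 12 = 105 pairs with u inside the window. This counts combinations and is not a probability. If the scheduled pre-injection value takes precedence, the count is 0.

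**Step 4. Same-day order.** Two values on one day have the same day difference, so the tie rule applies. A timed post-injection repeat is later by its clock time. An untimed one is set to 23:59 and so also counts as later, even if it was in fact made before the injection.

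**Step 5. Size, by assumption.** The documents give no frequency. If one patient's selected BCVA is d letters lower than the scheduled value, the raw arm mean moves by d/n. With the planned arm sizes:
- Active, n = 20: 5/20 = 0.25 to 15/20 = 0.75 letters.
- Sham, n = 10: 5/10 = 0.5 to 15/10 = 1.5 letters.

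SAP 6.1 reports 32 patients enrolled in the MD part without a split by arm, so actual denominators may differ slightly.

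**The case against.** The strongest reply is that this is an edge case in exploratory analyses. It needs an unscheduled eye assessment to exist, and after a visit on or past the planned day only a same-day one can win. No hypotheses are tested (Protocol 7.2). The MD primary endpoint is drug-related AEs, which SAP 6.7 keeps outside the windows. All individual values are listed and individual profiles plotted, so a displaced value may be noticed. A drop of 15 letters is large: a loss of more than 15 is itself a dose limiting criterion, and Protocol 1.2 reports no such events in the 12 single-dose patients. All of this stands and limits the weight of the point. It does not change which value the rule selects.

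Four stronger readings are tempting but not supported.
- **Bias against active.** A reader might infer that true injections prompt more poor unscheduled values. Protocol 4.1.5 makes all procedures before and after the injection identical for sham, so antisepsis, anaesthesia and dilation do not differ. Needle entry and drug do differ, so balance is not assured, but no passage shows an excess of checks in either arm or gives a direction for retinal thickness.
- **Mislabelled PK troughs.** The title of Table 6.7: 1 names PK, but the MD samples at Visits 3 and 4 are planned only before dosing: "PK and [REDACTED] samples must be taken before next drug administration; no window afterwards". A stray later sample would be a deviation. SAP 6.2 has sampling-time deviations reviewed, Protocol 7.3 lets affected data be excluded, and PK parameters use actual times.
- **Distorted FAZ endpoints.** The FAZ secondary endpoints are at Visits 5 and 7, where no injection is given. With complete data, an MMRM with visit-specific treatment and baseline effects gives the same treatment estimates at those visits as separate regressions per visit. Visit 3 and 4 values can reach them only when visits are missing.
- **Unscheduled values always count as later.** The 23:59 rule applies only when the time is missing. A timed repeat made before the injection keeps its order.

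**Conclusion.** The point holds as a gap in a stated rule. As written, SAP 6.7 selects a post-injection value over the scheduled pre-injection one at Visits 3 and 4 in circumstances that the plan itself allows for. It bears directly on change from baseline in BCVA and central retinal thickness at those two visits, and on FAZ at Visits 5 and 7 only indirectly, through the MMRM when visits are missing.

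How often this happens, and which arm it would favour, cannot be derived from the documents. The illustration of 0.75 letters (active) or 1.5 letters (sham) assumes one affected patient with a 15-letter difference and the planned arm sizes. The conclusion also assumes that same-day values are ordered by clock time, which the SAP implies but does not spell out. The MD primary endpoint and the baseline value are not affected.

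**What to change.** Add two sentences to SAP 6.7. For ophthalmic efficacy endpoints at Visits 3 and 4, the scheduled assessment made before that visit's injection or sham injection is selected. An unscheduled value is used only if the scheduled one is missing, and only if it precedes that injection. Post-injection unscheduled values stay in the safety listings.

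The cost is those two sentences and a flag in the analysis data set, with no effect on patients or data collection. The rule should be fixed in writing and not settled case by case, because Protocol 4.1.6.1 has the sponsor's statistician and data manager working unmasked. On this ground no change is needed for PK or for Visits 5 to 7.

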## FLOW CHART II (MULTIPLE DOSING PART)

Trial Periods	Screening Period	Treatment Period			Follow-up Period		End of Study
		1 	2	3	4	5	
Study Day/ Week	Duration 3 to 28 days	1	29 Week 4	57 Week 8	85 Week 12	113 Week 16	155 Week 22
Time window for visits (days)		none	±3	±3	±7	±7	±7
Informed consent	X						
Informed consent Aqueous sampling (optional)	X						
Demographics	X						
Medical history	X						
Physical examination (including weight)	X				X		
Vital signs	X	X	X	X	X	X	X
Laboratory tests	X	X	X	X	X	X	X
12 lead-ECG 	X	X	X	X	X		
Review of in-/exclusion criteria	X	X					
Dose Assignment		X					
Randomization		X					
IVT drug administration/Sham injection		X	X	X			
Pregnancy test 	X S	X S	X U	X U	X U	X U	X U
██████████		X	X		X		
PK Sampling 		X	X	X	X	X	X
Optional Aqueous sampling 		X		X		X	X
BCVA testing	X	X	X	X	X	X	X
SD-OCT	X	X	X	X	X	X	X
OCT Angiography	X	X	X	X	X	X	X
Fundus Photo	X	X	X	X	X	X	X
Slit lamp and intra-ocular pressure (IOP)	X	X	X	X	X	X	X
██████████		X	X	X	X	X	X
All AEs/SAEs/AESIs	X	X	X	X	X	X	X
Concomitant therapy	X	X	X	X	X	X	X
Completion of patient participation 							X

- (1) Screening visit should be performed in two visits. After Informed consent is obtained, visual acuity testing, SD-OCT, OCT Angiography and fundus photography should be performed and sent to central reading service. If patient is eligible based on the results from the reading centre, the patient should return to complete the rest of the screening. In case of scheduling difficulty for certain patients, screening can be performed in one visit. If screening is done as one visit, fundus photography should be performed in line with other ophthalmological examinations.
- (2) See Section [5.2.5](#); the ECGs are to be recorded shortly before the PK sampling at the respective time points: Appendix [10.1](#)
- (3) Pregnancy testing: serum pregnancy test ( $X_S$ ) is done at screening and on day 1 if more than a week elapsed between screening and day 1, and at the other visits as a reflex when urine testing ( $X_U$ ) is positive.
- (4) See separate flow chart for PK, ██████ and aqueous sampling (Appendix 10.1)
- (5) Completion of patient participation also needs to be completed if the patient withdraws prematurely following assignment to dose level (see Section [3.3.4](#))

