7.8.2 Laboratory data

The analyses of laboratory data will be descriptive in nature and will be based on BI standards [BI-KMED-BDS-HTG-0042] (12).

Laboratory data will be analysed qualitatively via comparison of laboratory data to their reference ranges. Values outside the reference range as well as values defined as possible clinically significant will be flagged in the data listings.

To support analyses of liver related adverse drug effects, the frequency of patients with AST and/or ALT $\geq 3xULN$ combined with a total bilirubin $\geq 2xULN$, and the frequency of patients with AST and/or ALT $\geq 10xULN$, will be displayed. This analysis will be based on standardized laboratory values. A graphical analysis of the ALT and total bilirubin during the on-treatment period will also be performed; the so called eDISH plot. In the graph, for each subject, the peak total bilirubin is presented as a fold increase over the ULN against the peak ALT as a fold increase over the ULN, on a log10 scale. The measurements displayed or total bilirubin and ALT may, or may not, occur on the same date. Two reference lines, $2xULN$ for total bilirubin and $3xULN$ for ALT, are drawn onto the graph in order to divide the plane into four quadrants. Normal cases are in the lower left quadrant, potential DILI cases are in the upper right quadrant (Hy's Law quadrant), while the lower right quadrant is known as the Temple's corollary range (ALT $\geq 3xULN$ and total bilirubin $< 2xULN$).

Clinically relevant findings in laboratory data will be reported as adverse events if judged clinically relevant by the investigator, and will be analysed as such.

It is the investigator's responsibility to decide whether a lab value is clinically significant abnormal or not (at the RPM/DBLM at the latest).

Descriptive statistics of laboratory data including change from baseline will be calculated by visit based on the worst value of the patient at that visit.

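### SAP 6.7 gives two unreconciled visit rules for unscheduled laboratory values in the MD part, and one of them files values from Days 2 to 28 under Visit 2/Baseline

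*SAP*

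**What the plan says.** SAP 6.7 sets a general rule for the MD part after a short list of exceptions: "All other safety and efficacy measurements will be assigned to visits based on extended time windows around the planned visit dates". The windows relevant here are in Table 6.7:1, whose title covers laboratory data: "Time window assignment of efficacy, safety lab, pk and vital signs measurements to visits for statistical analysis of the MD Part". The table closes the V2 (Baseline) window at Day 1 and opens the V3 (Week 4) window at Day 2. Its footnote fixes the count: "Days are counted relative to the day of first treatment, which is defined as Day 1". Where a window holds several values, the one nearest the planned day is used, "except for safety lab where the worst scenario is chosen".

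Directly above that table, the same section gives a second rule: "Unscheduled measurements of laboratory data will be assumed to be repeat measurements of the most recent scheduled measurement". It follows that "unscheduled measurements will be assigned to the planned time point of the previous scheduled measurement". This rule is not limited to the SRD part, is not called an exception to the windows, and carries no order of precedence.

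SAP 7.8.2 then calculates laboratory descriptive statistics, including change from baseline, by visit, "based on the worst value of the patient at that visit".

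**The concern.** An unscheduled MD laboratory value can be assigned to two different visits by two rules in one section, so two programmers who both follow the SAP could produce different by-visit tables.

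The early gap matters most. The protocol allows unscheduled visits at any time for safety reasons (6.2.3) and calls for an unscheduled blood test, if needed, when symptoms of hepatic injury arise without laboratory results (5.2.7.1.4). A test of that kind taken between the first injection and Visit 3 addresses something new. It does not repeat the Day 1 sample. Carry-back nevertheless attaches it to Visit 2, whose value is meant to be pre-dose. The first post-injection summary, Week 4, would then omit it.

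**Working it through.** No figure in the plan covers this point, so the check applies both rules to each calendar day and counts where they differ.

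**Inputs**
- Window rule (SAP Table 6.7:1): V2 up to Day 1; V3 Days 2–43; V4 Days 44–71; V5 Days 72–99; V6 Days 100–134; V7 from Day 135.
- Carry-back rule (SAP 6.7): the previous scheduled laboratory visit.
- Scheduled laboratory visits (protocol Flow Chart II, row "Laboratory tests X X X X X X X"): screening, then Days 1, 29, 57, 85, 113 and 155.
- Visit tolerances (Flow Chart II): ±3 days at V3 and V4, ±7 days at V5, V6 and V7.

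**Days on which an unscheduled test could fall, visits on planned days**

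Days 2 to 154 are 153 days. Removing the four visit days 29, 57, 85 and 113 leaves 149.

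**Days on which the rules differ**

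| Days | Window rule | Carry-back | Number of days |
|---|---|---|---|
| 2–28 | V3 (Week 4) | V2 (Baseline) | 27 |
| 44–56 | V4 | V3 | 13 |
| 72–84 | V5 | V4 | 13 |
| 100–112 | V6 | V5 | 13 |
| 135–154 | V7 | V6 | 20 |

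27 + 13 + 13 + 13 + 20 = 86, and 86/149 = 57.7%. The rules agree on the other 63 days.

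**Sensitivity to visit timing**
- All later visits at their early limits (Days 26, 54, 78, 106, 148): 146 − 4 = 142 eligible days. Differences: 24 + 10 + 6 + 6 + 13 = 59, and 59/142 = 41.5%. Days 2–25 go to V2 under carry-back.
- All later visits at their late limits (Days 32, 60, 92, 120, 162): 160 − 4 = 156 eligible days. Differences: 30 + 16 + 20 + 20 + 27 = 113, and 113/156 = 72.4%. Days 2–31 go to V2 under carry-back.

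In all three cases, every day between the first injection and Visit 3 goes to V2 under carry-back and to Week 4 under the windows. A value on Day 10, for example, is Week 4 by one rule and Baseline by the other.

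**Which outputs depend on the assignment**
- By-visit descriptive statistics with the worst value per visit (SAP 7.8.2): exposed.
- Baseline reference: defined in SAP 6.7 as the last measurement before first administration, so a post-dose value should not replace it.
- Potentially clinically significant values and AEs: SAP 6.7 states that their analysis is not by visit.
- eDISH plot: uses each subject's peak over the on-treatment period (SAP 7.8.2).
- Listings: individual values of all patients are listed (SAP 7), with out-of-range and possibly significant values flagged (SAP 7.8.2).

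**The case against.** The strongest reply is that the two rules need not conflict. The unscheduled rule is narrower, has its own rationale (follow-up or confirmation of a value), and could be read as a specific exception to the windows. It also follows an ECG passage that cites both flow charts, and the SRD part has no analysis windows, so it may be meant for the SRD part or for both parts. SAP 7.8.2 refers to a sponsor laboratory standard that is not available here and might settle the matter. All of this is possible, but the SAP states none of it. If the rule is an exception that applies to the MD part, the ambiguity goes but the filing of Day 2–28 values under Baseline becomes certain.

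The reply is right on the limits of the impact. Three stronger readings may tempt a reader, and the documents do not support them:
- *The change-from-baseline reference is contaminated.* The baseline definition in SAP 6.7 keeps it pre-dose. The fault lies in where the later value is placed.
- *A safety signal is hidden.* An abnormal Day 10 value should still appear in the analyses not based on visits, the listings and, where clinically relevant, the AE tables. Protocol 7.3.4 assigns measurements to treatments by planned time, so one might argue that a carried-back value slides into the screening period and out of the on-treatment displays. But SAP 6.1 starts the on-treatment phase at the time of first administration and presents laboratory tables for that phase, which should keep the value in.
- *Some 58% of unscheduled values are misfiled.* The count is of calendar days. Neither document says how many unscheduled tests to expect or when.

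The reply also has a fair point on the remedy. Carry-back keeps a confirmatory repeat with the test that it repeats, so removing it at every MD visit is a trade-off, not a correction.

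**Conclusion.** The concern holds, with limited reach. SAP 6.7 contains two rules that give different visits for the same unscheduled MD laboratory value on 86 of 149 non-visit days when visits fall on plan, and on 41.5% to 72.4% of such days when all visits sit at their early or late limits. Under carry-back, a value taken after the first injection and before Visit 3 is filed at Visit 2/Baseline. It is then absent from the Week 4 worst-value summary. The SAP does not say whether it would next drop out of the by-visit change-from-baseline tables or be shown under Baseline; these are the two plausible results, and neither is what the table should show.

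The exposure is confined to the by-visit descriptive laboratory tables. The MD primary endpoint counts patients with drug-related AEs, and the protocol tests no hypothesis (7.2), so no primary result depends on it. Within those tables, the MD arms are planned at 20 and 10 patients, so one misplaced extreme value can set a visit's maximum or minimum and move its mean.

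The conclusion assumes that the carry-back sentence applies to the MD part, as its placement under the MD text and above Table 6.7:1 suggests, and that no sponsor standard overrides it. The size in practice depends on the number and timing of unscheduled tests, which the documents do not give.

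**What to change.** Make two additions to SAP 6.7:
1. State which rule takes precedence for unscheduled laboratory values in the MD part.
2. State that no value taken after the first administration is assigned to Visit 2/Baseline, so that values from Days 2 to 28 go to Week 4 under Table 6.7:1.

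The simplest way to meet the first is to use Table 6.7:1 for all MD laboratory values, scheduled and unscheduled, with the worst-value selection already specified. Every day after Day 1 then maps to one visit, and 0 of the 149 days are in conflict. The second sentence is still worth having, because the table counts whole days and a post-dose sample on Day 1 itself would otherwise fall in the Baseline window.

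The downside is small: a confirmatory repeat may land in the next visit's window. A recheck on Days 44 to 56 of a Day 29 finding would count towards Week 8, and a recheck on Days 2 to 28 of an abnormal pre-dose value would count towards Week 4. If the sponsor prefers to keep repeats with the test that they repeat, carry-back can stay for later visits, provided that its precedence is stated and Visit 2/Baseline is closed to post-dose values.

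The cost is a sentence or two in the SAP and one programming rule. Data collection and patients are not affected.
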